The secondary variables analyzed were: the use of healthcare resources measured as the number of home visits by healthcare personnel (scheduled and unscheduled), average time hospitalized at home, exacerbations after discharge and readmissions for this reason. Other secondary variables: 1) degree of satisfaction with home care (Satisfad questionnaire¹⁰) and for the intervention group also a specific survey, consisting of four questions with answers using a five-level Likert scale (assessment from 1 to 5, from lower to greater satisfaction and / or need for help) and a fifth open-ended question about their experience with the monitor. 2) Measurement of anxiety and depression using the STAI questionnaire (trait-trend) in the home hospitalization phase. 3) Impact on well-being and quality of life using the CAT (COPD Assessment Test) questionnaire. 4) Therapeutic compliance through the Morinsky-Green-Levine questionnaire at the beginning and at the sixth month; additionally for the intervention group, adherence to telemonitoring was determined based on compliance with the protocolized shipments.

Comparative interventions:

The first phase of the study was hospitalization at home (with or without telemonitoring depending on the assigned group) and the second phase was follow-up after medical discharge (identical for both groups, without telemonitoring); with one consultation a month and another at 6 months. In these consultations, outpatient and / or hospital exacerbations were collected, as well as other study variables.

Control group (conventional home hospitalization):

** Visiting regime: a first visit is made in the hospital (doctor and nurse who will follow up), making a clinical evaluation and management of the bronchodilators.

The rest of the visits are daily at home and will initially be carried out only by the infirmary, except for the final visit in which the doctor accompanies him to discharge the patient, if he meets the following criteria:

- Clinical stability, with recovery from daily activities, with dyspnea similar to its baseline.
- Saturation levels > 90% with or without oxygen and lower requirements for short acting adrenergic beta2 agonists.
- Correct use of medication.

Constants are taken, physical examination, clinical evaluation and health education (involving knowledge of your disease, inhalation technique, therapeutic compliance, exercise respiratory, nutritional advice and smoking cessation if needed).

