The main hypothesis is to verify that after the early discharge, the health results caused by the experimental treatment (intervention) are not inferior to the reference treatment (control). The scientific literature states that the median of the “exacerbation-free time” of the reference treatment is 2 months, and therefore, the “non-inferiority” condition requires that the median in the experimental group be similar. It is considered appropriate to set a “noninferiority” limit of 0.60 units in multiplicative terms with respect to the reference treatment; In other words, an attempt will be made to demonstrate that the experimental treatment provides at least a median of the exacerbation-free time of not less than 1.2 months (36 days), if it is exacerbated before this period of time the study didn't comply the “non inferiority” condition. Thus, we calculated that a minimum sample of 58 patients per treatment group (in total 116) was required to ensure a power of 80% and a significance level of 5%. Exacerbation-free time was defined as the interval between discharge from the home and the moment of exacerbation, until the end of the study when it did not occur or in the event of loss of follow-up until the last recorded time. All analyzes were performed according to the principle of intention to treat.

The statistical analysis of the main variable was carried out using the Kaplan-Meier method and the statistical test of the log-rank test.

The comparison between the two groups was made with the Student t test for continuous variables and the non-parametric Mann-Whitney test when the normality test was rejected.

The statistical package used was Stata V.15.1.

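### The trial is designed and sized for non-inferiority with a 0.60 limit, but the planned primary test does not use the limit, and the only stated decision rule (36 days) has no confidence bound

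*Combined protocol and SAP*

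**What the plan says.** All the key text is in the Statistic analysis section of the combined protocol and SAP.

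- **Hypothesis.** The aim is to show that "the health results caused by the experimental treatment (intervention) are not inferior to the reference treatment (control").
- **Limit.** It is a "limit of 0.60 units in multiplicative terms with respect to the reference treatment". With a literature control median of 2 months, the experimental treatment must be shown to be one that "provides at least a median of the exacerbation-free time of not less than 1.2 months (36 days").
- **Decision rule.** The same sentence goes on to say that the non-inferiority condition is not met if exacerbation occurs earlier than that. No confidence bound is attached.
- **Sample size.** 58 per group, 116 in total, "was required to ensure a power of 80% and a significance level of 5"%. Sidedness, formula, event target and loss allowance are not given.
- **Analysis.** "The statistical analysis of the main variable was carried out using the Kaplan-Meier method and the statistical test of the log-rank test". The only other tests named are Student's t and Mann-Whitney, for continuous variables.
- **Follow-up.** Times are censored "until the end of the study when it did not occur or in the event of loss of follow-up". The end of the study is not defined there. Comparative interventions gives a schedule "with one consultation a month and another at 6 months" and adds: "In these consultations, outpatient and / or hospital exacerbations were collected".

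**The concern.** A log-rank test with no stated shifted null asks whether two curves are equal. A non-inferiority test asks whether the data exclude a ratio as low as 0.60. The limit sets the hypothesis and the sample size, then disappears from the primary test.

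The 36-day sentence does not fill the gap. Its subject is unclear: it could mean a patient or a group median. On its most sensible reading it compares a point estimate with a fixed number of days, so sampling error plays no part. The number is also absolute, whereas the limit is relative.

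At stake is the trial's main conclusion. As written, the plan does not lead to a non-inferiority claim with a known error rate, and two analysts could reach opposite conclusions from the same curves.

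**Working it through.** **Inputs from the documents:** limit 0.60, control median 2 months, 58 per group, power 80%, level 5%, last consultation at 6 months. **Assumptions not in the documents:** follow-up ends at 6 months, no losses, exponential times unless stated.

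**1. The plan's own sample size.** Let k = (z for the level + z for the power)². For 80% power, k = (1.645 + 0.842)² = 6.18 at one-sided 5%, and (1.960 + 0.842)² = 7.85 at two-sided 5%. The probability of an event by 6 months with a 2-month median is 1 − 2⁻³ = 0.875.

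| Formula | Events, one-sided 5% | Patients (÷ 0.875) | Events, two-sided 5% | Patients (÷ 0.875) |
|---|---|---|---|---|
| Schoenfeld, 4k / (ln 0.6)² | 94.8 | 108 | 120.3 | 138 |
| Freedman, k × (1.6/0.4)² | 98.9 | 113 | 125.6 | 144 |

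Freedman at one-sided 5%, with events rounded up to 99, gives 57 per group (114 in total), close to the stated 58 and 116. So the size is consistent with a one-sided 5% non-inferiority calculation on the 0.60 limit. This is an inference. Other combinations of formula and loss allowance also come close.

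**2. The 36-day rule on the observed median.** Put the true experimental median exactly at 1.2 months, where passing is an error. Each of the 58 patients then has probability one half of an event before 1.2 months. The Kaplan-Meier median is the 29th ordered time, so the rule passes if at most 28 patients have events earlier: P(Binomial(58, 0.5) ≤ 28) = (1 − 0.104)/2 = 44.8%. This does not depend on the shape of the distribution; simulation gives 44% to 46%.

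The rule also moves with the control median. If that were 3 months, 1.2 months would be a ratio of 1.2/3 = 0.40; if 1.5 months, 1.2/1.5 = 0.80.

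**3. If a non-significant log-rank test were taken as success.** The share of trials passing at a true ratio of 0.60 (two-sided 5%, 10,000 simulated trials per setting) is:

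| Setting | Passing |
|---|---|
| Exponential | 25% |
| Weibull, shape 0.7 / 1.5 | 58% / 2% |
| Log-normal, log-SD 1 / 1.5 | 30% / 61% |
| Exponential, 41 per arm (30% fewer patients) | 40% |
| Exponential, 12 months of follow-up | 23% |

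**4. An example.** With about 102 events (116 × 0.875 = 101.5), the standard error of the log hazard ratio is 2/√102 = 0.198. Under exponential times the 0.60 limit is a hazard ratio of 1/0.60 = 1.667. An observed hazard ratio of 1.40 gives p = 0.089, not significant. Its 95% upper bound is exp(0.336 + 1.96 × 0.198) = 2.06, a time ratio of 0.48, so the limit is not excluded. Non-inferiority would need an observed hazard ratio of at most 1.20 (one-sided 5%) or 1.13 (one-sided 2.5%).

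**5. What a bound against the limit achieves.** One form is a one-sided log-rank test after dividing all experimental times by 0.60. At one-sided 5% it passes 4.7% to 5.3% of trials at a true ratio of 0.60 under every common-shape distribution tried. If the control arm is exponential and the experimental arm Weibull with shape 0.7 or 1.5, it passes about 20% or 0.2%.

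Model-based power in the table is Φ(√events × 0.511/2 − z) with 101.5 events. Both rows take a true ratio of 1, exponential times and no losses.

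| Method | One-sided 5% | One-sided 2.5% |
|---|---|---|
| Rescaled log-rank (simulated) | 79% | 69% |
| Model-based bound | 82% | 73% |
| Ratio of medians, bootstrap (simulated) | 57% | 45% |

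**The case against.** The strongest reply is that the plan does contain a decision criterion, the 36-day sentence, and that Kaplan-Meier curves supply the median to which it applies. This stands as a matter of fact. A reader might infer that the plan never says how results become a non-inferiority conclusion; the documents do not support that. What they lack is error control for the rule they give.

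A reader might also infer that a non-significant log-rank result was to count as non-inferiority. The documents do not say so. The 25% figure therefore describes a hypothetical rule, and it depends heavily on the distribution. At Weibull shape 1.5 that rule passes about 2%, so it is not always too lenient.

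Thirdly, any particular repair is partly preference. The rescaled log-rank holds 5% only if the arms share a shape, and nothing in the documents supports that. The limit is worded on the median, and the method closest to that wording has much lower power. This stands too: the necessary correction is a bound against 0.60, and the method is open.

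The 6-month horizon is inferred from the visit schedule, but the 12-month run shows it matters little here.

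**Conclusion.** The point holds and must be fixed, because it concerns the primary hypothesis. The limit that defines success does not enter the planned test. The stated 36-day rule, read as a rule on the observed median, passes about 44% to 46% of trials with a true ratio of exactly 0.60 (58 per arm, control median 2 months, no losses before 1.2 months). Taking log-rank non-significance as success would pass about 25% with exponential times and 2% to 61% across the Weibull and log-normal shapes tried. Neither rule is set at the stated 5%, and the sidedness of that 5% is missing.

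Two stronger conclusions do not follow. The sample size is not shown to be wrong: it fits a one-sided 5% calculation, although the plan does not say that this was used. Nor do the documents show that a false non-inferiority claim was made, since they contain no results.

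**What to change.** - **Effect measure.** Name one for the primary analysis: the experimental-to-control time ratio, the ratio of medians, or a hazard ratio. The hazard-ratio limit of 1.667 corresponds to 0.60 only for exponential times. At Weibull shapes 0.7 and 1.5, a Cox bound against it has type I error of 18% and 0.2%.
- **Decision rule.** State the confidence level and sidedness, and declare non-inferiority only if the bound excludes the limit. Replace the 36-day rule with this, noting that 1.2 months is merely the limit at a 2-month control median.
- **Method.** One suitable choice is the rescaled log-rank test, with the ratio of Kaplan-Meier medians and a bootstrap interval alongside. The latter needs no equal shapes but has less power.
- **Existing methods.** Keep Kaplan-Meier as description and the ordinary log-rank test for superiority only.
- **Power.** Restate it for the chosen method and sidedness, using the figures in the last table of the working as a starting point.

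**Cost.** SAP wording and a short reanalysis in Stata of data already collected; no extra patients. The Protocol section describes the trial as carried out from March 2012 to July 2018, so the analysis must be labelled as specified after the fact. The stated 80% power may not hold: for the rescaled log-rank at one-sided 5% it ranges from 49% (Weibull shape 0.7) to 99% (shape 1.5), and is about 66% with exponential times if 30% of patients give no data.

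### No between-group method for post-discharge exacerbations and readmissions accounts for observation time, so if raw counts are compared and loss differs, the arm losing more patients can appear to have fewer events

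*Combined protocol and SAP*

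**What the plan says.** Under Study variables, the secondary resource-use outcomes begin with "the use of healthcare resources measured as the number of home visits by healthcare personnel (scheduled and unscheduled") and continue with "average time hospitalized at home, exacerbations after discharge and readmissions for this reason". Only home visits are clearly called a number. The form of the two event outcomes (count, yes/no or rate) is not stated.

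Under Comparative interventions, follow-up after discharge is the same in both arms and ends with a 6-month consultation. On data collection the text says: "In these consultations, outpatient and / or hospital exacerbations were collected". No other source of event data is named.

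Under Statistic analysis, the main variable has its own method: "The statistical analysis of the main variable was carried out using the Kaplan-Meier method and the statistical test of the log-rank test". Exacerbation-free time runs "until the end of the study when it did not occur or in the event of loss of follow-up until the last recorded time". For everything else the section says: "The comparison between the two groups was made with the Student t test for continuous variables and the non-parametric Mann-Whitney test", the latter when normality is rejected. All analyses follow intention to treat. No count, rate or categorical method is named, and there is no rule for incomplete follow-up in the secondary outcomes.

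The withdrawal criteria, under Participation criteria, include inability to use telemonitoring. The opening description of the trial says that withdrawn patients were not replaced.

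**The concern.** The plan expects loss to follow-up and deals with it for the primary variable, but the same patients also contribute to the secondary event outcomes. If their totals enter a t test or Mann-Whitney test as they stand, a patient last seen at month 1 with no events is treated exactly like a patient followed for 6 months with no events. The unobserved months then act as event-free months.

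Loss that is similar in both arms lowers both means and leaves the comparison fair. Loss that differs moves the comparison towards the arm with more loss. The plan contains one route to a difference, since only patients assigned to telemonitoring can be withdrawn for being unable to use it. In a trial meant to show that telemonitoring is no worse, an error in that direction would flatter the new arm on readmissions and repeat exacerbations, which are the outcomes a reader would look to for support.

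**Working it through.** **The plan's own figure.** The documents give no figure for these two outcomes. The only related one is the sample size of 58 per group. Freedman's formula with ratio 0.60, one-sided 5% and 80% power gives (1.645 + 0.842)² × (1.6/0.4)² ≈ 99 events. With a 2-month median in both arms, the probability of an event within 6 months is 1 − 2^(−6/2) = 0.875. Then 99/0.875 ≈ 113.1, or 57 per arm (114 in total) against the stated 116. The plan does not state its formula or sidedness, and other choices do not come as close. The agreement shows only that a 2-month median and a 6-month horizon are a fair basis for what follows.

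**Inputs from the plan:** 2-month control median; 6 months of planned follow-up; 58 per arm.

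**Assumptions:** constant event rate; loss unrelated to event risk; the loss percentages; the timing of loss.

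**Expected count.** The rate is ln2/2 = 0.3466 per month, so 6 months give 0.3466 × 6 = 2.08 exacerbations per patient.

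**Bias in the raw count ratio.** If a fraction f of an arm is lost and each lost patient forfeits on average a share m of the 6 months, the arm's mean count is multiplied by 1 − f·m. With no true difference, the ratio (arm 1 / arm 0) is (1 − f₁m)/(1 − f₀m). Loss spread evenly over 6 months gives m = 1/2; last contact at month 1 gives m = 5/6.

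| Loss, arm 1 vs arm 0 | Even over 6 months | All last seen at month 1 |
|---|---|---|
| 15% vs 5% | 0.925/0.975 = 0.95 | 0.875/0.958 = 0.91 |
| 20% vs 5% | 0.900/0.975 = 0.92 | 0.833/0.958 = 0.87 |
| 25% vs 5% | 0.875/0.975 = 0.90 | 0.792/0.958 = 0.83 |
| 15% vs 15% | 1.00 | 1.00 |

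The event rate cancels, so under the same assumptions these ratios apply to readmissions too, although the plan gives no readmission rate. In the equal-loss row both means are still too low, by 0.15 × 1/2 = 7.5% or 0.15 × 5/6 = 12.5%.

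**False-positive rate.** Simulated two-sided 5% rejection, 58 per arm, no true difference:

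| Scenario | t test | Mann-Whitney | Person-time rate ratio, robust variance |
|---|---|---|---|
| Even loss, 20% vs 0%, Poisson | 12.3% | 13.6% | 5.6% |
| Even loss, 20% vs 0%, strong overdispersion (gamma shape 1) | 7.7% | 8.5% | 6.3% |
| Even loss, 30% vs 10%, Poisson | 11.7% | 12.0% | 5.5% |
| Even loss, 10% vs 10%, Poisson | 4.5% | 4.4% | 4.8% |
| Month-1 loss, 20% vs 5%, gamma variance 0.5 | 11.3% | 13.9% | not run |

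The even-loss rows use 6,000 simulated trials each and the month-1 row 3,000. In the even-loss rows the person-time rate ratio stayed at about 1.00. For month-1 loss of 15%, 20% or 25% versus 5%, negative binomial regression with a log follow-up offset and dispersion estimated from the data gave rate ratios of 1.00 to 1.01 and rejection of 5.0% to 6.8% (600 trials each).

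**A real excess can be hidden.** If the true rate is 20% higher in an arm losing 30% evenly, against no loss in the other, the raw ratio is 1.2 × 0.85 = 1.02.

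**The case against.** The strongest reply is that the plan never says these outcomes are counts and never assigns them a test. The t test and Mann-Whitney sentence is written for continuous variables, so the provable gap is an outcome form and method left unstated. That stands, and for this reason the point is conditional on a raw-count comparison. It does not remove the problem. If the named tests do not apply, the plan has no between-group method for these outcomes, and a simple yes/no comparison would depend on observation time as well.

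Other points that stand:

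- Scoring unobserved months as event-free is an inference. Complete-case analysis or another rule is equally compatible with the text.
- Planned follow-up is identical in the two arms, and bias between arms needs unequal loss, which the documents do not quantify.
- Last contact at month 1 for every lost patient is the severe end of the range. The month-1 simulation also departs slightly from the plan's anchor: with a mean rate of ln2/2 and frailty variance 0.5, the median first event falls at about 2.4 months, not 2.
- The log-rank test is a between-group test that handles censoring, although it is assigned only to the main variable.

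A reader might infer that the telemonitoring arm was in fact favoured, or that the non-inferiority conclusion is unsafe. The documents support neither. They give no loss by arm, the arm losing more need not show fewer events (the 1.02 example), and the non-inferiority claim rests on exacerbation-free time, which is censored. No margin attaches to the secondary outcomes.

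**Conclusion.** The point holds in conditional form. The plan names no method that accounts for observation time in post-discharge exacerbations or readmissions. If they are compared as raw counts and loss differs between arms, the arm losing more can appear to have fewer events. With an assumed 20% versus 5% loss and no true difference, the count ratio would be about 0.92 (even loss) to 0.87 (all last seen at month 1). With equal loss it would be 1.00. These figures rest on a constant rate, loss unrelated to risk, and loss percentages that are assumptions; the true size and direction cannot be established from the documents. The effect is confined to supportive secondary evidence. The change is worth making because the remedy is cheap and the telemonitoring-specific withdrawal reason makes unequal loss plausible.

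**What to change.** State the form of each secondary event outcome, then its method:

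- **Numbers of exacerbations and readmissions:** negative binomial regression (or Poisson with robust standard errors) on treatment arm. The offset is the log of days from home-hospitalization discharge to last recorded contact, capped at the 6-month consultation. Report the rate ratio with its confidence interval and events per patient-month by arm.
- **Readmission as yes/no:** time to first readmission, censored at last contact.
- **By arm in all cases:** person-time observed, loss to follow-up, and the number of patients with no post-discharge observation. The last group cannot enter the offset model because the log of zero days is undefined. It may include patients withdrawn during home hospitalization for inability to use telemonitoring, so it must not disappear silently.
- **Variables with no exposure time:** keep the t test and Mann-Whitney test.

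The cost is a few sentences in the analysis section and one Stata command (nbreg with an exposure term). The last-contact date is already needed to censor the primary variable, and the sample size does not change. The model assumes a roughly constant rate and non-informative loss, and the interval is slightly wider. That is still a weaker assumption than treating unobserved time as event-free.

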Early Assisted Discharge for COPD Exacerbations With Telemonitoring.

ClinicalTrials.gov, NCT01951261.

Versión 1. 01/02/2012

**Department Pneumology Hospital Puerta de Hierro and Carlos III Health
Institute.**

**Reseachers: [name], [name], [name], [name].**

Protocol:

The TELEMED-COPD study is a randomized clinical trial with 2 parallel groups (both with early discharge; intervention group: home hospitalization with telemonitoring / control group: traditional follow-up based on face-to-face visits by healthcare personnel). It was carried out at the Puerta de Hierro Hospital from March 2012 to July 2018. Once the informed consent was given by the participants, they were randomly distributed between the two groups using a table of pseudo-randomized numbers in variable blocks generated by computer. The randomization sequence was kept hidden by the randomization system itself. Substitution of patients withdrawn from the study was not performed.

Participation criteria:

Patient admitted with exacerbation of COPD in the Pulmonology Service, with no age limit and who, after an initial phase of clinical stabilization not exceeding 4 days, meets the inclusion criteria: 1) Diagnosis of COPD (prior or during admission according to GOLD 2020), 2) absence of serious decompensated concomitant diseases, 3) arterial blood gas: pH > 7.35, pO₂ > 50 mmHg with O₂ at maximum 3 bpm, Oxygen saturation > 90%, pCO₂ < 55, 4) afebrile more than 48 h, 5) need for administration of maximum bronchodilators every 6 hours, 6) corticosteroids < 40mg / 12 hours, 7) chest radiograph without new onset pathology, 8) subjective improvement, and 9) adequate family environment.

Exclusion criteria: 1) Neoplasms or other end-stage chronic diseases, 2) alcoholism, 3) need for intravenous medication, 4) inability to understand the program and participate in it, 5) have required ICU care or need mechanical ventilation non-invasive during exacerbation, 6) institutionalized patient.

Withdrawal criteria: unsuccessful inability to use telemonitoring, complications derived from hospital admission or at the express request of the patient.

Study variables:

The main variable was the time to the first exacerbation after discharge (exacerbation was defined as an acute and sustained deterioration in the patient's clinical condition, greater than the daily fluctuation and requiring a change in the usual medication)

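### No method that accounts for follow-up time is named for exacerbations and readmissions after discharge; raw counts would favour whichever arm loses more patients

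*Combined protocol and SAP*

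**What the plan says.** All references are to the combined protocol and SAP.

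- **Study variables.** The secondary variables include "average time hospitalized at home, exacerbations after discharge and readmissions for this reason". The scale (count per patient, proportion with an event, or rate) is not fixed.
- **Statistic analysis, method.** After the primary analysis, one sentence covers group comparisons: "The comparison between the two groups was made with the Student t test for continuous variables", with a switch to "the non-parametric Mann-Whitney test when the normality test was rejected". No test for proportions, count model or person-time method is named.
- **Statistic analysis, follow-up.** Exacerbation-free time runs, "in the event of loss of follow-up until the last recorded time". No such rule is given for any secondary variable. All analyses are by intention to treat.
- **Comparative interventions.** Follow-up after medical discharge is the same in both arms and without telemonitoring, "with one consultation a month and another at 6 months".
- **Participation criteria, withdrawal.** One reason is "unsuccessful inability to use telemonitoring", which only the intervention arm can meet. Withdrawn patients are not replaced.

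**The concern.** The plan foresees loss to follow-up but deals with it for one outcome only. Exacerbations and readmissions accumulate over time, so a patient seen for two months has had less chance of an event than one seen for six. A t test or Mann-Whitney test on raw counts treats the two alike. If post-discharge loss differs between arms, the arm that loses more patients shows fewer events for a reason unrelated to treatment.

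The direction matters in a non-inferiority trial. If more telemonitoring patients were lost, raw counts would hide some or all of a true excess of exacerbations in that arm. These outcomes are secondary, so what is at stake is how the event burden and resource use are read, not the primary conclusion.

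**Working it through.** **The plan's own figure.** The plan states no figure for the secondary comparisons. Its sample size, 58 per group (116), is used here only as the arm size. It can be approximately reproduced with Freedman's formula at one-sided 5%, an assumption because sidedness is not stated:

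- Events = (1.645 + 0.842)² × [(1 + 0.60)/(1 − 0.60)]² = 6.18 × 16 = 98.9, so 99.
- Probability of an event in 6 months with a 2-month median and exponential times = 1 − 0.5^(6/2) = 0.875.
- 99/0.875 = 113.1, or 57 per arm (114), within 2 patients of 116.

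**Inputs for the check**

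- From the documents: 58 per arm, 6 months of planned follow-up in both arms, reference median of 2 months.
- Assumed, because the documents give no values: loss per arm, loss times uniform over the 6 months, counts stopping at loss, 1.5 events per 6 months and overdispersion 0.6. As a second setting, the rate implied by the 2-month median is used: (ln 2/2) × 6 = 2.08 events per 6 months.

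**Expected raw ratio.** With a proportion p lost at uniform times, mean follow-up is a fraction 1 − p/2 of the planned time. For telemonitoring (T) against control (C):

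raw ratio = true ratio × (1 − p_T/2)/(1 − p_C/2)

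- 5% vs 15%: 0.925/0.975 = 0.95
- 5% vs 25%: 0.875/0.975 = 0.90
- 5% vs 35%: 0.825/0.975 = 0.85
- 5% vs 25%, true ratio 1.3: 1.3 × 0.897 = 1.17
- Equal loss: factor 1, no bias

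**Error rates by simulation** (1.5 events, overdispersion 0.6, nominal two-sided 5%; ranges cover separate runs of the same scenario, Monte Carlo error about 0.4-0.8 percentage points):

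| Loss C / T | True ratio | Raw ratio | Rejects, t test | Rejects, Mann-Whitney | Rejects, follow-up offset |
|---|---|---|---|---|---|
| 5% / 15% | 1.0 | 0.95 | about 5-6% | about 5-6% | about 5-6% |
| 5% / 25% | 1.0 | 0.90 | 8-9% | about 9% | 5-6% |
| 5% / 25% | 1.3 | 1.17 | 11% | 8% | about 25% |
| 15% / 15% | 1.5 | 1.50 | 48-50% | 40-42% | 51-53% |

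**Second setting** (2.08 events, true ratio 1.0; false positives as t / Mann-Whitney):

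| Loss C / T | Raw ratio | Poisson counts | Overdispersion 0.7 |
|---|---|---|---|
| 5% / 15% | 0.95 | 7.2% / 6.9% | 5.5% / 5.5% |
| 5% / 25% | 0.90 | 11.5% / 12.4% | 8.6% / 9.5% |
| 5% / 35% | 0.85 | 20.5% / 22.5% | 12.3% / 14.0% |

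Events divided by person-time gave a ratio of 1.00 in every one of these scenarios.

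**Timing of the arm-specific withdrawal.** The telemonitoring equipment is installed on the first day at home and used only in the home phase, whereas these events are counted after discharge. The 5% vs 25% case was therefore rerun with the telemonitoring losses occurring before discharge and those patients simply missing. Rejection under the null was 4.8-5.7%, so there was no inflation. The expected raw ratio is then 1/0.975 = 1.03, not below 1.

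**The case against.** Four points can be made on the other side.

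1. **The plan does not say that counts are tested this way.** A reader might infer that it prescribes a t test or Mann-Whitney test on exacerbation counts. The sentence is worded for continuous variables, and the scale of these outcomes is left open. This stands: the firm finding is that no suitable method is specified, and the bias follows only if the one named rule is applied to raw counts.

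2. **Shorter follow-up in the telemonitoring arm is not established.** A reader might infer it from the withdrawal reason that only that arm can meet. Difficulty with the device would mostly show before the post-discharge clock starts. Such patients are then either followed under intention to treat or have no post-discharge data, and in neither case does a bias towards telemonitoring follow. Scoring the missing patients as zero events would create one, but the plan does not say that. This also stands: the criterion makes imbalance possible, no more.

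3. **The effect is small at modest imbalance.** At 5% versus 15% loss with overdispersed counts, false positives stay near nominal. This stands for the error rate, although the estimate is still shifted by about 5%.

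4. **The primary outcome is protected.** Time to first exacerbation is censored at last contact, so a reader should not conclude that the non-inferiority test shares this fault.

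The normality pre-test is a separate matter and does not cause the follow-up bias. Preferring a difference in means over a rank test for "average time hospitalized at home" or visit numbers is closer to a preference, and no size has been shown for it.

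None of this removes the gap: the plan has no rule for incomplete follow-up in two outcomes that depend directly on follow-up time.

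**Conclusion.** The concern holds as a conditional gap in specification. The plan names no method for exacerbations and readmissions that accounts for time at risk. If they are compared as raw counts and post-discharge loss differs between arms, the comparison is biased towards the arm with more loss.

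Under the assumed 1.5 events per 6 months, overdispersion 0.6 and uniform loss, a true ratio of 1.0 appears as 0.95 at 5% versus 15% loss and 0.90 at 5% versus 25%. The error rate is materially affected only in the second case. There, a true 30% excess appears as about 17%, and power to detect it is 8-11% against about 25% with the offset. With equal loss there is no bias. The cost is then power, mainly for Mann-Whitney: about 41% against 51% at a ratio of 1.5.

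The documents support neither a claim that the bias will occur nor a claim that it must favour telemonitoring. They give no loss rates, and they do not say whether withdrawn patients are still followed for events. Readmissions were not simulated separately. The direction of bias is the same for them, but the error rates above should not be carried over.

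**What to change.** - Define exacerbations and readmissions after discharge as event rates. Analyse each by negative binomial or overdispersed Poisson regression with log post-discharge follow-up time as offset, and report the rate ratio with its 95% interval.
- State whether withdrawn patients are still followed for events, and keep collecting those events where possible, in line with the stated intention to treat. An offset cannot help a patient with no post-discharge follow-up, and it assumes that loss is unrelated to a patient's event rate. Report numbers and timing of loss by arm so that both can be judged.

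The cost is a few lines of code and an assumption about dispersion. The model needs no new data, because the primary analysis already requires the discharge date and date of last contact.
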